9.1.1.1 Sampling Strategy for Pharmacokinetic Study

First dose pharmacokinetic study of ABT-888, Day 1 of ABT-888 and Radiation treatment Blood samples will be collected prior to the first dose of ABT-888 on day 1 of radiation treatment, and then at 0.5, 1, 2 and 6-8 hours after the first dose of ABT-888. Blood samples may be obtained either by repeated phlebotomies or through temporary or permanent intravenous catheters/devices. The pre-ABT-888 sample may be obtained at study entry, provided that the specimen is processed and stored appropriately per section 9.1.1.2.

For children who require sedation for radiation and are not able to take the p.o. medication due to local requirements for NPO prior to sedation, the pre-ABT-888 sample may be obtained at study entry or at any time prior to the first dose of ABT-888 (to be administered the night prior to first day of radiation treatment). Subsequent PK samples outlined above (at 0.5, 1, 2 and 6-8 hours after a dose of ABT-888) should be collected after the child awakens from sedation and after the second dose of ABT-888 is given on day 1 of radiation treatment.

Steady state pharmacokinetic study of ABT-888, Day 4 of ABT-888 and Radiation treatment Blood samples should be obtained prior to the A.M. ABT-888 dose on day 4 of radiation treatment, and then at 2 hours after the A.M. dose. Blood samples may be obtained either by repeated phlebotomies or through temporary or permanent intravenous catheters/devices.

For children who require sedation for radiation and must remain NPO in the morning, the day 4 samples should be obtained after the child awakens from sedation on day 4 and then at 2 hours after the day-4 ABT-888 dose has been given.

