8.1 ABT-888 (NSC # 737664)

Chemical Name: 1*H*-Benzimidazole-7-carboxamide, 2-[(2*R*)-2-methyl-2-pyrrolidinyl]-Other Names: Veliparib, A-861695.0 Classification: Poly (ADP-ribosome) polymerase (PARP) Inhibitor CAS Registry Number: 912444-00-9 Molecular Formula: $C_{13}H_{16}N_4O$ M.W.: 244.29

Mode of Action: ABT-888 is a potent oral PARP1/2 inhibitor whose pharmacological properties include high solubility (crosses the blood brain barrier), linear PK, and low potential drug-drug interactions. In vivo and in vitro, ABT-888 inhibits the formation of poly (ADP-ribose) (PAR) polymer and prevents the repair of DNA that is damaged by cytotoxic agents. Furthermore, ABT-888 can increase antitumor efficacy of temozolomide, cisplatin, carboplatin, cyclophosphamide, irinotecan, or radiation therapy.

[figure not shown]
Route of Administration: The oral solution can be administered with water or juice if needed. ABT-888 will be administered twice daily (~12 hours apart), Monday through Friday, during radiation therapy. The morning dose of ABT-888 should ideally be given 60-120 minutes prior to daily irradiation. For children who require sedation for irradiation and must remain NPO in the morning, ABT-888 may be given each night prior to bedtime, and the morning dose should be given shortly after the child recovers from sedation, adhering as closely to an every-12-hour schedule as possible. However, if permitted by the local sedation/anesthesia guidelines, ABT-888 may be given each morning prior to sedation, ideally 60-120 minutes prior to irradiation. See additional administration instructions in section 5.1. See **Appendix** D for calculated dose of ABT-888 capsules for patients taking capsules only.

[figure not shown]
During the maintenance therapy (starting on week 11 of protocol therapy), ABT-888 will be given twice daily (~12 hours apart), on days 1-5 of each 28-day course, with the morning dose of ABT-888 to be given 60-120 minutes prior to the morning temozolomide dose. The capsules should be swallowed whole without breakage. See Appendix E for the calculated dose for the ABT-888 capsules during maintenance for patients taking capsules only. ABT-888 capsules or the oral solution may be administered without regard to meals. If emesis occurs within 10 minutes of administration, the dose should be repeated.

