9. CORRELATIVE AND SPECIAL STUDIES

9.1 Laboratory Correlative Studies

9.1.1 Plasma Pharmacokinetics Studies

Participation in the pharmacokinetic studies is required during the Phase I portion of the study and strongly encouraged but optional during Phase II. Plasma pharmacokinetics samples will be obtained on days 1 (first dose) and 4 (steady state) during the first week of ABT-888 and

radiation treatment. If day 4 falls on a Saturday, please collect steady state PK samples on day 3. If day 4 falls on a Sunday, please collect steady state PK samples on day 5.

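### In children who are NPO for sedation, the day-1 first-dose PK curve follows the second dose and its starting concentration is not measured that day

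*Combined protocol and SAP*

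**What the plan says.** Section 9.1.1 schedules plasma sampling on "days 1 (first dose) and 4 (steady state"), and section 9.1.1.1 heads the day-1 part as the first-dose study. On the ordinary schedule a sample is drawn before the first dose "and then at 0.5, 1, 2 and 6-8 hours after the first dose of ABT-888".

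Children who cannot take oral medication because of local NPO rules have a separate schedule:

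- The pre-drug sample may be drawn as early as study entry; the permitted window is "any time prior to the first dose of ABT-888 (to be administered the night prior to first day of radiation treatment").
- The four post-dose samples are collected once the child is awake and "after the second dose of ABT-888 is given on day 1 of radiation treatment".
- On day 4, "the day 4 samples should be obtained after the child awakens from sedation on day 4 and then at 2 hours after" that day's dose.

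Sections 5.1.1 and 8.1 let a sedated child take the morning dose before radiation where local guidelines permit, so the separate schedule does not cover every sedated child. Otherwise section 8.1 asks for dosing "adhering as closely to an every-12-hour schedule as possible".

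Section 9.1.1.2 requires exact sample and drug-administration times on the transmittal form, without naming the previous evening's dose. Section 13.2.3 plans compartmental estimates, a NONMEM population model and a dose-proportionality ANOVA. It gives no rule for curves that follow a second dose.

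**The concern.** A true first-dose curve starts from zero, and a drug-free sample confirms that. In the NPO subgroup the sampled curve starts from whatever remains of the evening dose. The plan draws a sample where the answer is known to be zero and none where it is not. If such a curve is read as first-dose data, the residual drug is credited to the second dose, so AUC is too high and apparent clearance too low.

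ABT-888 pharmacokinetics is the second Phase I primary objective (section 1.1), and section 2.4.3 makes the sampling mandatory in Phase I. Section 13.1.1 studies three to six patients per dose level, so one or two such children can move a cohort summary.

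**Working it through.** **1. The two day-1 schedules side by side**

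| | Ordinary schedule | NPO for sedation |
|---|---|---|
| First dose | Day 1 of radiation | Evening before |
| Pre-drug sample | Before dose 1 | Before dose 1, possibly at study entry |
| 0.5, 1, 2, 6-8 h samples | After dose 1 | After dose 2 |
| Sample just before the sampled dose | Yes (drug-free) | None |

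The plan quotes no carry-over or half-life figure, so there is none to reproduce. The rest gives scale only.

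**2. Half-life implied by Table 2 (section 2.2.3.2), bolus approximation.** AUC0-12 is taken to be at steady state, as Cmax is. For one compartment with 12-hourly dosing, AUC/Cmax = (1 − e^(−12k))/k. The fraction left at 12 h is e^(−12k).

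| Table 2 column | AUC/Cmax (h) | k (per h) | Half-life (h) | Left at 12 h |
|---|---|---|---|---|
| Child 20 mg/m² | 1.55/0.379 = 4.09 | 0.229 | 3.0 | 6% |
| Child 15 mg/m² | 1.05/0.222 = 4.73 | 0.190 | 3.7 | 10% |
| Adult 40 mg | 1.87/0.348 = 5.37 | 0.158 | 4.4 | 15% |
| Adult 20 mg | 0.99/0.171 = 5.79 | 0.141 | 4.9 | 18% |

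In this model every concentration of the carried-over curve is e^(−12k) times its first-dose counterpart. AUC0-12 is therefore overstated by exactly the last column.

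**3. Allowing for oral absorption.** Take C(t) proportional to [ka/(ka − k)]·(e^(−kt) − e^(−ka·t)), with ka assumed to be 1, 2 or 4 per hour. Find the k for which the steady-state peak divided by the steady-state average matches Table 2, where Cmax × 12/AUC = 2.93, 2.54, 2.23 and 2.07. The overstatement is the first dose's AUC from 12 to 24 h divided by its AUC from 0 to 12 h.

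| ka (per h) | Half-lives, columns in the same order (h) | AUC0-12 overstated by |
|---|---|---|
| 1 | 1.5, 1.9, 2.3, 2.7 | 0.6%, 2%, 4%, 6% |
| 2 | 2.0, 2.5, 3.0, 3.4 | 2%, 4%, 7%, 10% |
| 4 | 2.4, 2.9, 3.6, 4.0 | 3%, 6%, 10%, 13% |

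Steps 2 and 3 together give about 1-18%. The two paediatric columns alone give 0.6-6% with absorption and 6-10% as a bolus.

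**4. Gap between doses.** The range 10-14 h is an assumption. In the bolus model the extremes are e^(−0.229×14) = 4% and e^(−0.141×10) = 24%.

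**5. Effect on clearance.** Concentrations at 0.5, 1, 2 and 7 h after dose 2 were generated with ka = 2 per hour and a 12 h gap, then fitted as a single dose starting from zero. CL/F came out at 0.94 of its true value for a 3 h half-life and 0.88 for 4 h. The 4 h case lies slightly beyond what Table 2 implies at that ka.

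**6. What the day-4 sample adds.** In the bolus model a steady-state trough exceeds the level just before dose 2 by a factor 1/(1 − e^(−12k)), which is 1.07 to 1.23. With absorption the factor is 1.00 to 1.14. A genuine day-4 trough would therefore bound the carry-over closely.

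**The case against.** The strongest reply is that the bias needs an analysis the plan does not describe. Compartmental and NONMEM models accept multiple-dose histories, exact drug times are to be recorded, and no non-compartmental first-dose AUC is planned. The site instructions say openly that these samples follow the second dose. This largely stands: the bias is conditional and correctable. It does not close the point, because the transmittal instruction does not name the evening dose, tube labels carry planned time relative to dosing without a dose number, and section 13.2.3 does not commit to entering both doses.

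A second reply is that day 4 already supplies a trough. That stands in part, by step 6. However, pre-dose timing after awakening is implied rather than stated. Section 9.1.1 also moves a Sunday day 4 to day 5, a Monday, which under Monday-to-Friday dosing may follow a weekend off drug.

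Third, the effect is small beside between-patient variation. Table 2 gives AUC coefficients of variation of 0.42/1.05 = 40%, 0.49/1.87 = 26% and 0.37/0.99 = 37%. Day-1 PK also drives no escalation rule in section 13.1.1, and the abstract names toxicity and safety as the Phase I primary endpoints. All of this stands and keeps the point minor.

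A reader might go further and infer that day-1 parameters in sedated children will be inflated and that age will be confounded with carry-over. The documents do not support this. Only children barred from the morning dose are affected, and their number is not given. Section 5.1.4.6 mentions very young patients as likely to need sedation, but section 13.2.3 plans no age comparison. Under the linear PK stated in section 8.1, fractional carry-over does not depend on dose, so the dose-proportionality ANOVA is disturbed only if the share of such children differs between dose levels.

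**Conclusion.** The point holds as an inexpensive improvement to sampling and analysis wording. For the NPO subgroup, the level at the start of the day-1 curve is not measured that day and the first-dose label does not fit.

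The 1-18% overstatement of AUC0-12 applies only if these curves are treated as first-dose data. It rests on a 12 h gap, a one-compartment model, assumed absorption rates, and half-lives of about 1.5-5 h inferred from Table 2. The paediatric columns there come from one and six children. The upper end comes from three adults under the bolus approximation. With oral absorption allowed for, the range is about 1-13%. It would be wrong to conclude that carry-over is wholly unobserved or that the planned PK results are biased as they stand.

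**What to change.** For children following the NPO schedule:

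- In section 9.1.1.1, take the existing pre-dose sample after awakening and immediately before the second dose, instead of at study entry.
- On the transmittal form, add the date and time of the previous evening's dose, and identify the curve as second-dose.
- In section 13.2.3, state that these curves are fitted with both doses and their recorded times before being pooled with true first-dose curves.

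The number of draws is unchanged and no change to dosing is implied. The cost is the loss of a drug-free assay blank in this subgroup, plus minor wording and form edits. In return, one sample gives a concentration roughly 12 h after the first dose, later than anything on the ordinary day-1 schedule. Where samples have already been collected, the labelling and analysis statements can still be adopted.

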9.1.1.2 Sampling Collection and Processing Instructions

Blood samples (a minimum of 2.5 ml for children < 12 kg, and 3-5 ml for children > 12 kg) should only be collected in potassium EDTA tubes, provided by AbbVie. All information about the PK kits and ordering instructions are available on the PBTC-033 members' website in the Protocol Specific Instructions/Forms section. Sites are to record the exact time that the sample is drawn along with the exact time that the study drug is administered on the PK Sample Transmittal form located in the PBTC-033 Protocol Specific Instructions/Forms section of the PBTC members' webpage.

9.1.1.3 Sampling Handling and Shipping Instructions

Samples should be immediately inverted 8 to 10 times to reduce the likelihood of clot formation and centrifuged within 30 minutes at sufficient speed and time to separate plasma (e.g. 1300 x g for 10 minutes). Plasma should be transferred to labeled cryovials (labels and cryovials provided by AbbVie) within one hour of collection and stored immediately at -20°C or colder.

Each tube must be labeled with the labels provided in the collection kits. These will include the patient's accession number, the study number, and the planned time of sampling relative to dosing. Data should be recorded on the Pharmacokinetic Sample Transmittal Form located on the PBTC-033 'Protocol Specific Instructions/Forms' section of the PBTC Members' webpage.

The transmittal form must accompany the sample(s).

Samples from day 1 and day 4 PK studies for each patient should be batched together and shipped via express carrier (Monday through Wednesday only). Samples are to be shipped at -20°C or colder (on dry ice) to:

Please ship each patient's PK samples as soon as the complete set has been collected rather than waiting to batch multiple patients' samples together. Please FAX the completed form to AbbVie Sample Receiving on the day of shipment. Also, be sure to include the completed PK Specimen transmittal form in the shipment as it will provide an inventory of the samples included in the shipment. PK samples must be shipped within 30 days of Day 4 sample collection in order to receive cost reimbursement.

9.1.1.4 Description of Pharmacokinetic Analysis

Plasma concentration of ABT-888 will be analyzed using a previously validated LC/MS/MS technique. These samples will be analyzed at AbbVie Laboratories, located in AbbVie Park, IL.

9.1.2 Correlative Biology Studies in PBMC

Participation in the correlative biology studies is strongly encouraged but optional.

9.1.2.1 *Collection of Specimen(s)*

Whole blood samples (a minimum of 5 ml for children < 12 kg, and 10 ml for children > 12 kg) should be collected in either ACDA (Acid citrate dextrose solution A; yellow top) or heparinized (sodium or lithium heparin; green top) tubes. Blood samples should be collected at the following time points:

- 1. Prior to start of first dose of ABT-888 and radiation treatment (sample may be collected at the time of study entry or any time prior to start of 1st dose of ABT-888)
- 2. On day 3-4 during the third week of ABT-888 and radiation treatment, 2 hours after the day-time dose of ABT-888; if day 4 falls on a Friday, collect this sample on day 3
- 3. On day 3-4 during the sixth week of ABT-888 and radiation treatment, 2 hours after the day-time dose of ABT-888; if day 4 falls on a Friday, collect this sample on day 3
- 4. On day 4 during the first course of maintenance ABT-888 and TMZ, 2 hours after the daytime dose of ABT-888; if day 4 falls on a Friday, collect this sample on day 3; if day 4 falls on a Sunday, collect this sample on day 5; if day 4 falls on a Saturday, collect this sample on day 2.

Record the exact date and time that the sample is drawn along with the exact time ABT-888 was administered on the Biologic Specimen Transmittal Form located on the PBTC-033 Protocol Specific Instructions/Forms section of the PBTC members' webpage.

If possible, avoid collecting samples on a Friday to avoid weekend sample shipment. If unavoidable, please contact Drs. [name] at [contact] ([contact]) or [name] at [contact] ([contact]) to arrange for Saturday delivery.

9.1.2.2 Sample Processing

No processing is required. Keep the whole blood at room temperature until the time of shipping.

9.1.2.3 Sample Labeling

Each tube must be labeled with the patient's accession number, the study number, the exact date and time the sample was drawn and the exact time that the drug was administered. Data should be recorded on the Biologic Specimen Transmittal Form located on the PBTC-033 Protocol Specific Instructions/Forms section of the PBTC members' webpage. The transmittal form must accompany the sample(s).

9.1.2.4 Shipping Instructions

Each sample should be shipped immediately on the day of collection. Samples should be stored at room temperature until shipment. Sample handling and shipping instructions are available on the PBTC-033 Protocol Specific Instructions/Forms section of the PBTC members' webpage. Samples should be shipped by priority overnight via express carrier (Monday through Thursday only).

[name]; Attention: [name] Feigin Center [name] Baylor College of Medicine Houston, TX 77030 [contact]

Prior to shipping, please contact Drs. [name] at [contact]([contact]) or [name] at [contact] ([contact]) for notification of sample shipment.

9.1.3 Correlative Biology Studies in Tumors

Participation in correlative studies for tumor specimens is optional but strongly encouraged.

Frozen Tumor

9.1.3.1 *Collection and Processing*

If biopsied tumor is available, the sample should be frozen in liquid nitrogen as soon as possible and shipped on dry ice. Data should be recorded on the Biologic Specimen Transmittal Form located on the PBTC 033 Protocol Specific Instructions/Forms section of the PBTC members' webpage.

9.1.3.2 Labeling and Shipping

Samples should be labeled with the patient's PBTC accession number and the date of surgery. Frozen tumor specimens should be shipped Monday through Thursday only. The specimen should be accompanied by the Correlative Biology Study Form and shipped by overnight carrier to:

[name]; Attention: [name] Feigin Center [name] Baylor College of Medicine Houston, TX 77030 [contact]

Prior to shipping, please contact Drs. [name] at [contact]([contact]) or [name] at [contact] ([contact]) for notification of sample shipment.

9.1.3.3 Sample Analysis

PARP activity will be measured using an established ELISA assay for PAR formation by AbbVie Laboratories.⁴⁶ NHEJ activity will be evaluated by an enzymatic assay,⁴⁷ and protein levels of Ku 70, Ku 80, DNA-PK, BRCA 1, BRCA 2, Rad51, and ATM will be measured by Western analysis in [name] laboratory.

FFPE Slides

9.1.3.4 Collection and Processing

Fifteen to twenty unstained PLUS glass slides, containing 5-micron thick tumor sections from FFPE tumor blocks will ALSO be requested in the event that frozen tumor specimens submitted are of insufficient amount or inadequate quality.

9.1.3.5 *Labeling and Shipping*

Slides should be labeled with the patient's PBTC accession number and the date of surgery. The Correlative Biology Study Form located on the PBTC-033 Protocol Specific Instructions/Forms section of the PBTC members' webpage should be completed and shipped with the specimens. Slides should be shipped Monday through Thursday only. The slides should be shipped at room temperature to the address listed in 8.3.2. Prior to shipping, please contact Drs. [name] at [contact]([contact]) or [name] at [contact] ([contact]) for notification of shipment.

9.1.3.6 Sample Analysis

Immunohistochemical staining of PARP, Ku 70, Ku 80, DNA-PK, BRCA 1, BRCA 2, Rad51, and ATM will be performed by standard techniques in [name] laboratory at Baylor College of Medicine, Houston, Texas.

9.1.4 Urine Biomarkers

Participation in the urine biomarker study is strongly encouraged but optional.

9.1.4.1 *Sampling Strategy*

Urine will be collected at time of enrollment (pre-treatment), post ABT-888 plus radiation then at the time of each scheduled MRI. Urine will be collected throughout the time that each patient is receiving protocol treatment until disease progression.

9.1.4.2 Sample Collection

10-30 milliliters of urine will be collected in a specimen cup and immediately placed in ice. The specimen can remain on ice in the original container for 1-2 hours until transfer to a freezer for storage (-20 Celsius). Samples should be maintained at -20 C until shipped. Urine can be collected as a mid-stream catch while voiding or can be collected from a urimeter if the child is catheterized. It is necessary to keep the urine refrigerated to prevent the degradation of peptides. The MMPs are particularly sensitive to warmer temperatures and other enzymes within the urine will break down biomarkers if not inactivated by refrigeration.

9.1.4.3 Sample Labeling

Each urine specimen must be labeled with the patient's accession number, the study number (PBTC-033) and the date collected. Data should be recorded on the Urine Specimen Transmittal Form located on the PBTC-033 Protocol Specific Instructions/Forms section of the PBTC members' webpage. The transmittal form must accompany the sample(s).

9.1.4.4 Shipping Instructions

Samples must be shipped monthly from the site to the laboratory to receive cost reimbursement. The sample collection and shipping dates must be documented in the eCRF. All samples should be forwarded via FedEx, Monday through Thursday, by completing the internet form at http://www.fedex.com/us/ and requesting FedEx to email the laboratory. Fed Ex account information for the shipment of samples can be obtained on the PBTC website. Weekend deliveries are not permitted. All urine specimens along with a completed Urine Specimen Transmittal Form should be placed within a Styrofoam shipping package with dry ice and mailed to the attention of [name].

[name] Children's Hospital Boston Karp Research Building, 12th Floor [name] [contact] Email: [contact]

9.1.4.5 Description of Urine Biomarker Assay

All samples will be analyzed for the presence or absence of each of the 8 biomarkers. Zymography will be performed to analyze for MMP-2, MMP-9 and MMP-9/NGAL in a blinded fashion by the laboratory examiner and recorded as a positive or negative result, following a protocol well-established in our laboratory which has been validated in the literature.39

Zymography

Samples will be frozen immediately after collection and stored frozen (-20C) until assay. Aliquots of each sample will be centrifuged at 4,000 rpm for 5 min at 4C and the supernatants collected. Urine samples (30 uL) will be mixed with buffer consisting of 4% SDS, 0.15 mol/L Tris (pH 6.8), 20% (v/v) glycerol, and 0.5% (w/v) brom-phenol blue. Samples will be applied, without boiling, into wells of a 4% acrylamide Laemmli stacking gel/10% SDS-acrylamide separating gel containing 0.1% (w/v) gelatin (Life Technologies, Inc.) on a mini gel apparatus. Gels will be run at 15 mA/gel during stacking and at 20 mA/gel during the resolving phase at room temperature. After electrophoresis, the gels will be soaked in 2.5% Triton X-100 with gentle shaking for 30 min at ambient temperature with one change of detergent solution. The gels will then be rinsed and incubated overnight at 37°C in substrate buffer [50 mmol/L Tris-HCI buffer (pH 8), 5 mmol/L CaCl2, and 0.02% NaN3,]. After incubation, gels will be stained for 15 to 30 min in 0.5% Coomassie Blue R-250 in acetic acid, isopropyl alcohol, and water (1:3:6); destained in acetic acid, ethanol, and water (1:3:6), and photographed. The presence or absence of each species (MMP-2, MMP-9, MMP-9/NGAL) will be recorded and relative intensities (if present) noted.

ELISA

ELISA will be used to establish quantitative levels of each of the 8 biomarkers. Kits will be obtained from the manufacturers (R&D systems and Bioplex/Bio-Rad). Specimens, standards and reagents will be prepared according to manufacturer's instructions. Protein concentration will be determined via the Bradford method using bovine serum albumin as the standard. Results will be recorded as ng/ml or pg/L.

